**If the patient meets all inclusion and does not meet any exclusion criteria:**

- Call IVRS/IWRS to register visit to randomize the patient and receive the first IMP kit number assignment and NIMP (NASONEX) boxes if needed.
- Administer SNOT-22, VAS (for rhinosinusitis), reduced sense of taste severity, QoL (EQ-5D), and ACQ-6 (for patients with asthma).
- Health care resource utilization via e-CRF.
- Administer smell test (UPSIT).
- Obtain blood samples (prior to IMP) for:
  - Hematology laboratories (see [Section 9.4.2](#) for details),
    - Note: Anti-ds DNA antibody will be tested if ANA is positive ( $\geq 1:160$  titer).
  - Serum dupilumab concentration, and anti-drug antibodies,

- Hepatitis B viral load for patients in Japan (or other countries/regions if there is local regulatory requirement) who are HBsAg negative and HBsAb positive at V1,
- Tuberculosis test if required by local regulation,
- Stored DNA sampling, stored serum, and stored whole blood RNA, for those patients who have signed a specific informed consent form.
- Perform urine sampling for biomarkers and creatinine.
- Obtain serum and plasma for biomarkers, see [Section 9.5.2](#).
- [REDACTED]
- [REDACTED]
- Perform blood sampling for total IgE.
- Remind patient to bring the e-diary/NPIF meter to the next visit.
- Reminder: sexually active female patients of reproductive potential are required to practice an acceptable contraception (as defined in [E 15](#) or local protocol amendment in case of specific local requirement) during the entire study duration, while taking dupilumab and for 12 weeks after the last IMP dose. Sexually active male patients should be reminded that if their partner is a woman of childbearing potential, their partner should consider protection by acceptable method(s) of birth control.
- Administer IMP:
  - Patients are monitored for at least 30 minutes (or minimum time required by your local regulator) after the end of administration of IMP for any signs or symptoms of a hypersensitivity reaction,
  - Throughout the study, SC injection sites will be alternated between the 4 quadrants of the abdomen (avoiding navel and waist areas) or upper thighs or upper arms, so that the same site is not injected twice consecutively. Injection in the upper arms can only be performed by a person trained for 4 injections (caregiver trained by Investigator or delegate) or health care professional, but not the patient themselves. This instruction pertains to the day of the first dose is injected as well as the administration of q2w injections. Detailed instructions for transport, storage, preparation, and administration of IMP are provided to the patient,
- NIMP:
  - Ensure that the patient has sufficient quantity for dosing up until the next visit, knowing that one MFNS bottle contains sufficient doses for either 2 weeks of BID treatment or 4 weeks of QD treatment. Dispense MFNS if needed. Instruct patient to record usage in the e-diary.
- Advise patients with comorbid atopic conditions (such as asthma) not to adjust their treatment without consultation with their physicians.
- Schedule appointment for next visit.

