- E 19. Known or suspected history of immunosuppression, including history of invasive opportunistic infections (eg, histoplasmosis, listeriosis, coccidioidomycosis, pneumocystosis, aspergillosis), despite infection resolution; or unusually frequent, recurrent or prolonged infections, per Investigator's judgment.
- E 20. Active tuberculosis, latent untreated tuberculosis or a history of incompletely treated tuberculosis or non-tuberculous mycobacterial infection will be excluded from the study unless it is well documented by a specialist that the patient has been adequately treated and can now start treatment with a biologic agent, in the medical judgment of the Investigator and/or infectious disease specialist. Tuberculosis testing would be performed on a country

by country basis according to local guidelines if required by regulatory authorities or ethic committees.

- E 21. Evidence of acute or chronic infection requiring treatment with systemic antibacterials, antivirals, antifungals, antiparasitics, or antiprotozoals within 4 weeks before V1 or during the run-in period, or significant viral infections within 4 weeks before V1 that may not have received antiviral treatment.
- E 22. Live attenuated vaccinations within 4 weeks prior to Visit 1 or planned live attenuated vaccinations during the study (Refer to [Appendix A](#)).
- E 23. Patients with active autoimmune disease and/or patients using immunosuppressive therapy for autoimmune disease (eg, Hashimoto's thyroiditis, Graves' disease, inflammatory bowel disease, primary biliary cirrhosis, systemic lupus erythematosus, multiple sclerosis, and other neuro-inflammatory disease, psoriasis vulgaris, rheumatoid arthritis), or patients with high titer autoantibodies at V1 who are suspected of having high risk for developing autoimmune disease at the discretion of the Investigator or the Sponsor.
- E 24. History of malignancy within 5 years before V1, except completely treated in situ carcinoma of the cervix, completely treated and resolved nonmetastatic squamous or basal cell carcinoma of the skin.
- E 25. Known or suspected alcohol and/or drug abuse.
- E 26. Patients with a history of a systemic hypersensitivity reaction, other than localized injection site reaction, to any biologic drug.

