#### **9.4.3 Hepatitis screening**

Hepatitis screening: HBsAg, hepatitis B surface antibody (HBsAb), HBcAb including HBcAb IgM and total, hepatitis C virus antibodies (HCVAbs). In case of results showing HBsAg (negative) and HBcAb total or HBcAb IgM (positive), a HBV DNA testing must be performed prior to randomization to determine eligibility. In case of results showing HCVAbs (positive), a HCV RNA testing must be performed prior to randomization to determine eligibility.

For patients in Japan (or other countries/regions if there is local regulatory requirement) who are HBsAg negative and HBsAb positive at V1, Hepatitis B viral load will be tested at V2, V7, V8, and V10.

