### 10.1 VISIT SCHEDULE

This section describes how the visits are carried out, in chronological order (according to the flow chart [Section 1.2](#) and identical to the order shown in the e-CRF):

The clinical trial consists of three periods, using an add-on therapy approach to INCS:

- Run-in Period (28 days+/- 3 days; V1).
- Randomized treatment period (up to 52 weeks +/- 3 days; Visits 2-10).
- Post-treatment Period (12 weeks; +/- 3 days V11).

The study visits occur on the planned dates (relative to the first injection), as scheduled. The visit schedule should be adhered to within the  $\pm 3$  day visit window.

If a patient is prematurely discontinued from treatment, every attempt should be made for the patient to return to the study site as soon as possible after last IMP administration to perform all assessments planned at the EOT visit and patients will be asked and encouraged to return to the study site for the visit scheduled as described in [Section 10.3.1](#) (early discontinuation) for a 12-week follow up.

Prior to all screening assessments, after discussion of participation in the study, the written consent form [REDACTED] must be signed and dated (see [Section 12.2](#)). At selected sites, requirements for collection of samples for a nasal biomarkers substudy will be included in a separate written informed consent.

Although the screening assessments for this study are grouped under the heading of a single visit in this protocol, it is possible for them to be performed over more than 1 site visit if necessary, as long as the run-in period window prior to Day 1 (V2) is respected. These patients do not need to sign a new consent form and be allocated a new patient number within this same window.

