#### Rescreening

Patients that fail screening between V1 and V2 may be rescreened for study eligibility only once for the following criteria:

- They do not meet the inclusion criteria for a weekly average NC >1 at V2

- They had an acute illness such as acute sinusitis, nasal infection or upper respiratory infection (E07). These patients can be rescreened only after complete resolution of symptoms
- They took one of the prohibited treatments listed in [Section 8.8.1](#) between V1 and V2.

Patients that are re-screened must sign a new consent form and all of the V1 procedures must be repeated (refer to [Section 8.4](#) for further instructions related to re-screening) unless a prior assessment is performed within the time frame permitted prior to study entry or the V1 baseline CT scan of sinuses and spot urine for biomarker sampling were performed. Patients with positive test for HIV or hepatitis will not be allowed for rescreening.

Note, no waivers will be approved for randomization; all patients must fulfil all eligibility criteria before randomization into the study.

If certain dynamic laboratory tests do not meet the eligibility criteria, these laboratory assessments may be repeated, at the discretion of the investigator, if it is judged to be likely to return to acceptable range for study inclusion within the screening visit window.

For patients who do not fulfil other exclusion criteria, rescreening should be discussed with the Sponsor. In all cases, a given patient can only be re-screened only once.

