#### 10.1.2 Visit 2 (Week 0): Randomization

- PRO patient administration in the e-diary: Daily symptoms of NC, loss of smell and anterior and posterior rhinorrhea.
- Inquire about AEs/SAEs and background therapy tolerability.
- Review and record all medication use with start date and dose in e-CRF.
  - Check for use of prohibited medications.
- Download e-diary/NPIF meter and check compliance with use of the mandatory background therapy (MFNS), as defined as:

- $\geq 80\%$  of total number of prescribed “stable dose” sprays taken during the run-in period. Compliance is verified based on MFNS use recorded in the patient e-diary.
- Remind patient to bring the device to the next visit.
- Confirm patient eligibility:
  - Review V1 nasal endoscopy results from central reader to confirm that patient has a score 5 or more and at least 2 each side.
  - Perform and review local endoscopy to confirm that patient has still a score 5 or more and at least 2 each side and record result in e-CRF. If the patient does not have the required scores at the V2 nasal endoscopy, the inclusion criteria are not fulfilled and the patient should not be randomized.
  - Record symptoms of sinusitis, and check the severity average of the last 7 days before visit 2 is  $>1$  for the symptoms: nasal congestion/obstruction.
  - Record spirometry result from V1 and record FEV1 (liters and predicted), FVC and FEF 25-75 result in the e-CRF. Confirm eligibility for patients with FEV1  $>50\%$ .
  - Check patient compliance with daily diary.
- Investigator to assess eligibility for nasal polyp surgery.
- Perform ECG (refer to [Section 9.4.6](#)).
- Obtain urine  $\beta$ -HCG pregnancy test if WOCBP. In case of positive test a serum pregnancy test to confirm the pregnancy should be performed as soon as possible. Pregnancy will lead to definitive screen failure.
- Measure vital signs (blood pressure, heart rate, respiration rate, body temperature, weight).
- Review all Inclusion/Exclusion Criteria to reconfirm eligibility.
  - Reminder that patients receiving prohibited medications described in [Section 8.8.1](#), including rescue with intranasal corticosteroid drops, SCS, or surgery for NP during the run-in period, are NOT eligible for randomization.

**If entry criteria are not met, call IVRS/IWRS to register the visit and screen-fail the patient. Refer to [Section 8.4](#) for details regarding re-screening.**

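### The only visit list that names the tuberculosis test places it after the eligibility check and the randomization call, so a required result would be missing when exclusion E 20 is applied

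*Protocol*

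**What the plan says.** Protocol 7.2.3, E 20, excludes "Active tuberculosis, latent untreated tuberculosis or a history of incompletely treated tuberculosis" (and non-tuberculous mycobacterial infection) unless a specialist has documented adequate treatment. It adds that testing is done country by country where authorities or ethics committees require it. It names no visit and does not say when the result must be available.

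Protocol 10.1.2 (Visit 2) is the only visit list with the test: "Tuberculosis test if required by local regulation". Earlier in that list comes the eligibility step, "Review all Inclusion/Exclusion Criteria to reconfirm eligibility", followed by the instruction to screen-fail patients who do not qualify. A bold line then opens a block for patients who meet every criterion. Its first item is "Call IVRS/IWRS to register visit to randomize the patient and receive the first IMP kit number assignment". The tuberculosis test is in the blood samples further down that block, and the first injection comes later in the same block.

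Protocol 1.2, footnote o, says only that local tuberculosis testing takes place at baseline where required. The Rescreening text in 10.1 says that "no waivers will be approved for randomization; all patients must fulfil all eligibility criteria before randomization into the study".

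**The concern.** The testing sentence sits inside an exclusion criterion, so the test exists to decide eligibility. Its neighbours in the Visit 2 blood draw mostly serve other purposes: drug concentration, anti-drug antibodies and stored samples are baseline material, and hepatitis B viral load is a repeated measurement. A test that decides eligibility but is drawn after randomization cannot inform the decision it is meant to support. Even an immediate result would come after the randomization call.

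A patient could therefore be randomized and injected before a required test shows an E 20 exclusion. SAP 2.2.1 counts randomizing an ineligible patient as a randomization irregularity, and under SAP 2.3.1.1 the patient stays in the intent-to-treat population. Protocol 4.5 manages infection as a theoretical risk, partly through exclusion. Protocol 10.3.3 requires permanent discontinuation for opportunistic infection, including tuberculosis, but gives no specific instruction for a positive baseline test reported after dosing.

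**Working it through.** The plan gives no figure to reproduce; the check is of sequence and coverage.

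**Order of steps in Protocol 10.1.2**
1. Confirm eligibility; urine pregnancy test; review of all criteria.
2. Screen-fail if criteria are not met.
3. Bold line: continue only if all criteria are met.
4. Randomization call and first kit assignment.
5. Questionnaires and smell test.
6. Pre-dose blood samples, including the tuberculosis test where required.
7. Urine and biomarker samples, reminders.
8. First injection.

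E 20 is applied at step 1 and the sample is drawn at step 6. Section 10.1 introduces the visit descriptions with "This section describes how the visits are carried out, in chronological order".

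**Is the test named anywhere else?**
- 10.1.1 (Visit 1) lists hematology, chemistry, hepatitis, HIV, antinuclear antibody and chest X-ray. Its only mention of tuberculosis is the note that Japan needs a chest X-ray if there is no chest imaging within 3 months.
- No later visit list names the test, and neither do the SAP laboratory variables (2.1.4.3).
- Footnote o places it at baseline, but footnote i of the same flow chart uses baseline for Visits 1 and 2 together, so this does not fix the visit.

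**How comparable tests are handled**
- Hepatitis, HIV and antinuclear antibody samples are drawn at Visit 1.
- Section 9.4.3 states, for a specified serology pattern, that "a HBV DNA testing must be performed prior to randomization to determine eligibility", and sets the same rule for hepatitis C RNA.
- The Visit 2 pregnancy test comes before the bold line.
- Japan's chest X-ray, meant to exclude suspected active or untreated latent tuberculosis, is placed at Visit 1.

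**Timing**
- As listed, the sample and the first dose fall at the same visit: 0 days.
- If drawn at Visit 1, using the 28 ± 3 day run-in (1.2, footnote a): 28 − 3 = 25 to 28 + 3 = 31 days before Visit 2.

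**Scope**
- Countries in SAP 2.5.6: Japan 1 + Latin America 3 + East Europe 2 + Western Countries 8 = 14.
- The documents do not say which require the test, so the range is 0 to 14. Without a positivity rate, no patient count can be derived.

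**The case against.** The best defence is that bullet order within 10.1.2 is not binding. The sentence on chronological order can be read as ordering the visits, not the items within a visit. The list also departs from the protocol's own sequence rules: endoscopy appears before SNOT-22 and the smell test, although footnote j puts it after all other efficacy assessments. On this view a site must read 10.1.2 together with E 20 and the rule against waivers, and would test during run-in. Section 10.1 allows this for screening assessments, since "it is possible for them to be performed over more than 1 site visit if necessary".

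That a site may test earlier without deviating stands. But the conclusion does not depend on bullet order alone: the bold line separates steps taken before eligibility is settled from steps taken after, and the test is on the wrong side of it. The rule against waivers forbids the outcome, yet nothing says that this particular result must be in hand.

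Three further points stand and limit the claim:
- No country is identified as requiring the test. The one authority request described, Japan's, is met by chest imaging at Visit 1.
- E 20 can also be judged from history, specialist documentation and imaging, so only the test result is missing.
- The hepatitis contrast is less clean than 9.4.3 suggests, because footnote o and 10.1.1 say the confirmatory tests may be done. The other comparisons are unaffected.

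**Conclusion.** The concern holds. Followed as written, 10.1.2 leaves a required tuberculosis test result unavailable when E 20 is checked and when the patient is randomized, contrary to the rule that all criteria be met first. This is a misplaced procedure, not an absence of tuberculosis screening. It matters only where the test is required and only at sites that follow the Visit 2 list literally. Its size in patients is unknown. It bears on participant safety and on avoidable randomization irregularities; it does not affect the co-primary estimates or the type I error rate. It should be corrected because the remedy is small and the intended sequence is clear from the rest of the protocol.

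**What to change.** 1. Move the tuberculosis test from the post-randomization block of 10.1.2 to the Visit 1/run-in blood sampling list in 10.1.1, beside HIV and hepatitis.
2. State in flow chart footnote o that, where testing is required, the result must be available before randomization.
3. Add review of that result to the Visit 2 eligibility confirmation, ahead of the randomization call.

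The cost is protocol wording. The same sample is taken about four weeks earlier, at a visit that already draws screening blood. The downside is that some patients who later fail screening will have been tested.

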### 10.1.3 Visit 3 (Week 2)

- PRO Patient administration in the e-diary:
  - Daily symptoms of NC, loss of smell and anterior and posterior rhinorrhea,
  - VAS for rhinosinusitis,
  - Reduced sense of taste symptom severity score.
- Administer smell test (UPSIT).
- Inquire about AEs/SAEs and background therapy tolerability.
- Collect NIMP boxes
- Record all medication use with start date and dose in the e-CRF.
  - Check for use of prohibited medications.
  - Complete rescue medication/surgery page (s) of e-CRF. Use of oral steroids for rescue treatment of worsening nasal polyps or for another reason will be captured by the Investigator (or designee) on the appropriate page(s) of the e-CRF page and the date and dosing information (daily dose, duration, INN) will be informed. Details on planned date for surgery, type, and outcome (whenever possible) of surgery will be recorded in a specific e-CRF page. If surgery is performed during the study treatment period or follow-up an AE or SAE page will be completed.
- Call IVRS/IWRS to register visit and obtain next IMP kit number assignment and NIMP (NASONEX) box(es) if needed or report potential definitive IMP stop.
- Download e-diary/NPIF meter and review the data; remind patient to bring the device to the next visit.
- Perform blood sampling for serum dupilumab concentration.
- Administer IMP (one SC injection).
  - Patients will be monitored at the study site for a minimum of 30 minutes (or minimum time required by your local regulator) after the injection.
- NIMP:
  - Ensure that the patient has sufficient quantity for dosing up until the next visit, knowing that one MFNS bottle contains sufficient doses for either 2 weeks of BID treatment or 4 weeks of QD treatment. Dispense MFNS if needed. Instruct patient to record usage in the e-diary.
- Schedule appointment for next visit.
- Remind the patient to withhold the last dose of salbutamol/albuterol or levosalbutamol/levalbuterol for at least 6 hours prior to arriving at V4.

### 10.1.4 Visit 4 (Week 4)

- PRO Patient administration in the e-diary:
  - Daily symptoms of NC, loss of smell, and anterior and posterior rhinorrhea,
  - SNOT-22,
  - VAS for rhinosinusitis,
  - Reduced sense of taste symptom severity score,

- ACQ-6 (for patients with asthma).
- Inquire about AEs/SAEs and background therapy tolerability.
- Collect NIMP boxes
- Record all medication use with start date and dose in the e-CRF.
  - Check for use of prohibited medications,
  - Complete rescue medication/surgery page (s) of e-CRF. Use of oral steroids for rescue treatment of worsening nasal polyps or for another reason will be captured by the Investigator (or designee) on the appropriate page(s) of the e-CRF page and the date and dosing information (daily dose, duration, INN) will be informed. Details on planned date for surgery, type, and outcome (whenever possible) of surgery will be recorded in a specific e-CRF page. If surgery is performed during the study treatment period or follow-up an AE or SAE page will be completed.
- Call IVRS/IWRS to register visit and obtain next IMP kit number assignment and NIMP (NASONEX) box(es) if needed or report potential definitive IMP stop.
- Download e-diary/NPIF meter and review the data; remind patient to bring the device to the next visit.
- Perform spirometry (for patients with asthma) and record FEV1, FVC and FEF 25-75 result in the e-CRF.
- Administer smell test (UPSIT).
- Measure vital signs (blood pressure, heart rate, respiration rate, body temperature, weight).
- Perform nasal endoscopy and send to Central Reader.
- Perform blood sampling for serum dupilumab concentration.
- Obtain urine  $\beta$ -HCG pregnancy test if WOCBP. In case of positive urinary test the study treatment will be withheld and a serum pregnancy test to confirm the pregnancy should be performed as soon as possible. Pregnancy will lead to definitive treatment discontinuation in all cases.
- Administer IMP (one SC injection).
  - IMP can be administered by the patient or caregiver under the supervision of the Investigator or the designee,
  - Patients will be monitored at the study site for a minimum of 30 minutes (or minimum time required by your local regulator) after the injection.
- NIMP:
  - Ensure that the patient has sufficient quantity for dosing up until the next visit, knowing that one MFNS bottle contains sufficient doses for either 2 weeks of BID treatment or 4 weeks of QD treatment. Dispense MFNS if needed. Instruct patient to record usage in the e-diary.
- Schedule appointment for next visit.

